The aims of this pilot study are to (1) determine the feasibility and acceptability of the M-MILK intervention by nurses and parents, (2) determine the feasibility of recruitment and retention, (3) obtain variability data for sample size estimation, and (4) evaluate the charges and costs of the NICU hospitalization and 2 months CA care between the M-MILK and control groups. M-MILK will be considered feasible if M-MILK is implemented by nurses or parents after every hands-on care and during the beginning of a full gavage feeding at least 90% of the time. The M-MILK acceptability by nurses and parents will be determined via M-MILK Acceptability Questionnaire. Recruitment and retention will be considered feasible if at least 50% of infants approached for participation enrolled, 90% of infants completed all inpatient data collection, and at least 50% of infants completed post-discharge follow-ups.

V. Administrative Organization

Participants will be enrolled in the Neonatal Intensive Care Unit (NICU) at Loyola University Medical Center (LUMC) (Maywood, IL). The inpatient components of the study protocol will be conducted in the NICU at LUMC. The post-discharge follow-up components of the study protocol will be conducted via phone/zoom interview. Data storage and management will be carried out via REDCap (version 10.4.0, Vanderbilt University) and a secured research network drive, hosted by the Loyola University Chicago (Maywood, IL).

Upon sample collection, buccal swab and fecal samples will be labeled only with study ID numbers and collection date, and stored in a locked cabinet in a locked laboratory at Loyola University Chicago (LUC) Center for Translational Research and Education (CTRE). All samples will be stored at room temperature. Quarterly, the buccal swab samples and fecal samples will be securely transported in a biospecimen transfer container (Saf T Pak, Austell, GA) via car to Rush University Medical Center Genomics and Microbiome Core Facility (Rush) (Chicago, IL) for processing and analyses. A Service Agreement between LUC and Rush will be submitted through LUC Research Portal.

VI. Study Design

a. Design

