DNA methylation of NR3C1 & HSD11B2	
We will evaluate DNA methylation in buccal cell DNA collected at baseline, 34 weeks PMA, NICU discharge, and 2 months CA, as an index of early life toxic stress. A trained research team member will be collecting, transporting, and storing the samples. We will collect two buccal swab samples from each infant at each visit using Isohelix DNA Buccal Swabs (Boca Scientific, Westwood, MA) before feeding to avoid contamination. The buccal swab samples will immediately be placed in a storage tube with a DNA stabilizer Dri-Capsule (Boca Scientific, Westwood, MA). The samples collected will then be transported to a laboratory at the Loyola University Chicago Center for Translational Research and Education (Maywood, IL). All samples will be stored at room temperature. Quarterly, the buccal swab samples will be securely transported in a biospecimen transfer container (Saf T Pak, Austell, GA) via car to Rush University Medical Center Genomics and Microbiome Core Facility (Chicago, IL) for processing and analyses. DNA will be extracted from buccal swab samples using the Maxwell® RSC Buccal Swab DNA Kit (Promega, Madison, WI) implemented on an automated Promega RSC device. The DNAm status for both the NR3C1 exon 1F and HSD11B2 promoter regions will be assessed using quantitative bisulfite amplicon sequencing using an Illumina MiSeq sequencer. Preparation of the bisulfite-converted DNA for sequencing will be accomplished with primers for NR3C1 and for HSD11B2, as described,¹¹ employing a two-stage polymerase chain reaction protocol.⁶⁰ Using the Illumina MiSeq sequencer, we will be able to sequence the entire targeted region, including the 13 NR3C1 CpG sites in the 1F region and the 4 HSD11B2 CpG sites. These sites are associated with neuroendocrine system regulation, including the HPA axis, and cortisol reactivity in rodent and human studies.^{21,61-63} Bisulfite conversion controls will be included with each sequencing run and will also be assessed for non-CpG 'C's. Samples with conversion rates below 93% will be re-processed. Libraries will be prepared in technical triplicate from each bisulfite converted DNA template, and if the replicates differ by $> 10\%$, the sample analysis will be repeated. Unmethylated CpG sites will be converted to UpG (TpG upon PCR amplification) by bisulfite treatment. The percent methylation at any nucleotide coordinate will be determined by the ratio of C residues (derived from 5-methylcytosine) to C+T residues (derived from 5-methylcytosine plus cytosine, respectively) at any position within the NR3C1 and HSD11B2 genomic DNA sequence. In addition, the methylation status of each read will be assessed individually by counting the number of methylated CpG sites observed within that read and summed to assess average methylation status in each amplicon. The percent DNAm at the NR3C1 and HSD11B2 promoters and at each CpG site will be quantified using CLC genomics workbench (Qiagen) software package. DNAm data will be analyzed as a
	T0, T1, T3, T4 Buccal samples

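### Methylation is computed without a stated correction for incomplete bisulfite conversion, so accepted samples can read up to 7 points too high, and conversion that varies between samples adds technical noise

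*Combined protocol and SAP*

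**What the plan says.** The relevant text is in the protocol, Section VII.a.vi.1 (Measures), Table 1, row on DNA methylation of NR3C1 and HSD11B2.

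- Acceptance limit: "Samples with conversion rates below 93% will be re-processed".
- How conversion is checked: "Bisulfite conversion controls will be included with each sequencing run and will also be assessed for non-CpG 'C's".
- What is assumed of unmethylated sites: "Unmethylated CpG sites will be converted to UpG (TpG upon PCR amplification) by bisulfite treatment". No allowance is made for failure.
- The estimator: percent methylation is "determined by the ratio of C residues (derived from 5-methylcytosine) to C+T residues".
- Replication: "Libraries will be prepared in technical triplicate from each bisulfite converted DNA template", with a repeat if replicates differ by more than 10%.

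The row ends by making methylation a continuous outcome, in total for each promoter region and for each CpG site. Section IV lists as Aim 3 to "obtain variability data for sample size estimation", and Section IX repeats that the variability of the study variables feeds the planned R01. No section says that measured conversion is used to adjust the methylation value or enters an analysis as a covariate.

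**The concern.** Attributing every C to 5-methylcytosine is right only when conversion is essentially complete. An unmethylated cytosine that escapes conversion is also read as C. The plan assesses conversion, but the only use it states is the decision to re-process. A sample that passes carries its unconverted fraction into the outcome.

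The triplicates do not protect against this. They are prepared after conversion from one template, so they share its error and agree with one another.

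At stake are the reported level of methylation and its SD. The pilot is meant to deliver the SD. If conversion differs between samples, two infants with identical methylation get different values, and that difference is counted as biological variability.

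**Working it through.** **Inputs.** From Table 1: the 93% floor and the C/(C+T) estimator. From Section VI.a: 6 infants per group. The documents do not give the true level or SD of methylation or the spread of conversion rates, so those below are assumptions. The plan has no derived figure here to reproduce; 93% is a set limit.

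**Step 1: artefact in one sample.** A fraction m of cytosines is methylated and reads as C. Of the remaining 1-m, a fraction 1-c fails to convert and also reads as C.

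observed = m + (1-m)(1-c), so artefact = (1-m)(1-c).

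At the floor, c = 0.93:

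| True m | Observed | Artefact (points) |
|---|---|---|
| 0% | 7.00% | 7.0 |
| 2% | 8.86% | 6.86 |
| 5% | 11.65% | 6.65 |
| 10% | 16.3% | 6.3 |
| 30% | 34.9% | 4.9 |
| 50% | 53.5% | 3.5 |
| 80% | 81.4% | 1.4 |

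At c = 0.99 the artefact is at most 1 point. The 7-point bound covers accepted samples only; the plan does not say what happens to one that fails again after re-processing.

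**Step 2: two samples with the same truth.** With m = 2%, conversion of 93% gives 8.86%. Conversion of 99.5% gives 0.02 + 0.98 x 0.005 = 2.49%.

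**Step 3: effect on variance.** With c and m independent:

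Var(observed) = E(c)² Var(m) + (1-E(m))² Var(c) + Var(m) Var(c).

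Assume c uniform over 93% to 99.5% and mean m = 2%. Then E(c) = 0.9625 and E(c)² = 0.926. SD(c) = 6.5/√12 = 1.88 points. The technical term has SD 0.98 x 1.88 = 1.84 points and variance 3.38 points². The third term adds less than 0.001 to each ratio. Observed over true variance:

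- true SD 1: 0.926 + 3.38/1 = 4.31
- true SD 2: 0.926 + 3.38/4 = 1.77
- true SD 3: 0.926 + 3.38/9 = 1.30
- true SD 5: 0.926 + 3.38/25 = 1.06

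The ratio falls below 1 once the true SD exceeds about 6.8 points.

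**Step 4: other patterns of conversion.** If every sample sits at 93%, the SD is multiplied by 0.93 and only the level moves up. If conversion is uniform over 98% to 100% with mean m of 5%, a true SD of 2 points is observed as 2.05.

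**Step 5: arm comparison.** If conversion is unrelated to arm, the expected difference is multiplied by E(c), so it is attenuated but not shifted. Under the Step 3 assumption, artefact alone gives the arm difference a standard error of 1.84 x √(2/6) = 1.06 points.

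**Step 6: does a correction work?** Solving Step 1 for m gives m = (observed - (1-c))/c. At c = 0.93, an observed 11.65% returns (0.1165 - 0.07)/0.93 = 5%, and 34.9% returns 30%. This is exact only if c is known without error and is the same at CpG and non-CpG sites.

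**The case against.** **The floor is not the expected rate.** A reader might infer that values are typically 7 points too high. The documents do not support that. They give neither the distribution of conversion nor the methylation level at these genes, and 7 points needs both a sample at the floor and a nearly unmethylated site. This stands; 7 points is only a ceiling.

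**Inflation of the SD is not general.** It requires conversion to vary between samples and the true SD to be small. With constant conversion, or a true SD above about 7 points, the observed SD is slightly too small. This also stands.

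**No arm bias is shown.** A reader might infer a spurious treatment effect. Section VII's Procedures text has data collected in the same manner in both groups, and one core facility processes all samples. Nothing links conversion to arm.

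**The R01 need not be mis-sized.** Aim 3 and Section IX speak of variability in general and do not name methylation as the sizing endpoint. If the R01 used the same uncorrected assay, the uncorrected SD would be the one to plan with, and the loss would be efficiency. In addition, a pooled variance on 10 degrees of freedom has a 95% interval of about 0.49 to 3.08 times its estimate, so much of the range above lies within the pilot's own imprecision. That limits the consequence, but does not justify leaving in a removable error.

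**Silence is not proof.** The row relies on cited methods, a named software package and a core facility whose procedures are not in the documents. The supportable statement is that no correction is stated. The non-CpG sentence can also be read as applying to the controls alone. The next sentence gives samples their own conversion rates, so a per-sample rate is a fair inference, but one from the same amplicon is not stated.

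**Conclusion.** The point holds as a limited one. On the plan's own acceptance rule and estimator, methylation is raised by (1-m)(1-c), at most 7 points in an accepted sample, and the replicate check cannot show it. That much needs no outside figure.

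The effect on variability is conditional. The ratios of about 4.3, 1.8, 1.3 and 1.06 rest on an assumed uniform spread of conversion from 93% to 99.5%, mean methylation of 2%, and true SDs of 1, 2, 3 and 5 points. With conversion near 99% the effect is small. True differences are attenuated by the factor c, with no expected direction of bias between arms.

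A reader might also infer that 93% is the wrong floor and should be raised. The documents offer no basis for choosing another value, and correction addresses the artefact whatever the floor. Methylation enters none of the feasibility criteria in Section IV, so those conclusions are unaffected. This is a cheap improvement to an outcome measure, not a flaw that threatens the pilot.

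**What to change.** Add to the methylation row of Table 1, and refer to it in Section IX:

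- Each sample's percent methylation, by region and by CpG site, is corrected as (observed - (1-c))/c, with c estimated from that sample's own non-CpG cytosines. Corrected values are used for group comparisons and for the R01 variability estimates.
- Small negative corrected values, which will occur near zero because c is estimated, are kept when means and SDs are computed. Truncating them would bias both.
- Uncorrected values are reported as a sensitivity analysis.
- The conversion rate is reported by arm and visit. This would show whether conversion is in fact unrelated to arm, and whether it drifts across the quarterly shipments in a way that could look like change over time.

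The cost is one formula and slightly more bioinformatics work. If per-sample non-CpG rates are already produced, as the re-processing rule implies, no new data are needed; the plan should confirm this. The price is an assumption that conversion is equal at CpG and non-CpG sites, which should be stated. If the core facility already corrects for conversion, one sentence saying so and giving the method closes the point.

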More than 60,000 infants are born between 22 to 32 weeks gestation age (very or extremely premature) annually in the US. Approximately 11% of them develop comorbidities, i.e., oral feeding difficulty, failure to thrive, delayed neurodevelopment, and maladapted parent-infant interaction. As part of the Neonatal Intensive Care Unit (NICU) hospitalization, very and extremely preterm infants inevitably endure early life toxic stress, e.g., parental separation, painful procedures, sleep fragmentation, harmful hospital organisms, and antibiotic therapy, without adequate protective buffers. Early life toxic stress results in adverse epigenetic modifications of glucocorticoid-related genes (DNA methylation of NR3C1 and HSD11B2) and dysbiosis (altered gut microbiome), both impairing neurodevelopment. These adversities further exacerbate the risk of comorbidities and inappropriate brain development during sensitive periods of neuroplasticity. Evidence suggests adverse epigenetic modifications and dysbiosis may set a life-long trajectory of risk for chronic health conditions, i.e., mental health disorders, cardiometabolic and immunologic diseases. Hence, it is a clinical and scientific priority to test an early NICU intervention to attenuate stress-related adverse epigenetic modifications and dysbiosis. Prior research has paved the way for a potential early NICU intervention as follows. Human milk influences the structure and relative abundance of healthy gut bacteria, i.e., short-chain fatty acid (SCFA)- and lactate-producing bacteria (e.g., *Bifidobacterium* and *Lactobacillus*), and neurodevelopment. Maternal nurturing, e.g., licking and grooming (in rodents), and breastfeeding and touch (in humans), promotes neurodevelopment, reduces stress, and reverses stress-related epigenetic modifications. Building on what is known, the multisensory early oral administration of human milk (M-MILK) intervention by nurses or parents is designed to provide an enjoyable and nurturing experience for infants, through a safe and consistent infant-guided provision of human milk droplets, given orally as early as 22 weeks postmenstrual age. M-MILK is implemented after every hands-on care and during the beginning of a full gavage feeding. The objective of our planned NIH R01 randomized controlled trial is to examine the efficacy of M-MILK from birth to 2 months corrected age, and the mechanisms whereby this may occur. We propose the M-MILK pilot study (N = 20): a 2-group, 10 per group, parallel design, and longitudinal randomized controlled trial in preterm infants who are born between 22 to 33 weeks gestational age. M-MILK will begin on day 3 of life. We will measure outcomes using validated methodologies: maternal postpartum depressive symptoms via the Edinburgh Postnatal Depression Scale, parent stress via the Parental Stressor Scale: NICU, parent discharge readiness via the Screening and Multi-disciplinary Risk Assessment Scale & Parent Activation Scale, neurodevelopment via the Neurobehavioral Assessment of the Preterm Infants and Ages & Stages Questionnaire-3, oral feeding skills via the Early Feeding Skills Assessment and NeoEAT, parent-infant interaction during feeding via the Nursing Child Assessment Satellite Training-Feeding Scale and Postpartum Bonding Questionnaire, DNA methylation of NR3C1 and HSD11B2 via buccal samples, and gut microbiome via fecal samples. Outcomes will be measured at baseline, 34 weeks postmenstrual age, discharge, and 2 months corrected age. The aims of this pilot study are to (1) determine the feasibility and acceptability of the M-MILK intervention by nurses and parents, (2) determine the feasibility of recruitment and retention, (3) obtain variability data for sample size estimation, and (4) evaluate the charges and costs of the NICU hospitalization and 2 months CA care between the M-MILK and control groups. M-MILK will be considered feasible if M-MILK is implemented by nurses or parents after every hands-on care and during the beginning of a full gavage feeding at least 90% of the time. The M-MILK acceptability by nurses and parents will be determined via M-MILK Acceptability Questionnaire. Recruitment and retention will be considered feasible if at least 50% of infants approached for participation enrolled, 90% of infants completed all inpatient data collection, and at least 50% of infants completed post-discharge follow-ups. This pilot study will inform our R01 application regarding the feasibility and acceptability of M-MILK and sample size estimation.

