The M-MILK pilot study ($N = 12$) is a 2-group, 6 per group, parallel design, and longitudinal randomized controlled trial. We will recruit preterm infants who are born between 22 to 33 weeks gestational age. We will compare the outcomes between the M-MILK and attention control groups. Infants will be enrolled into the study as soon as possible after they are admitted to the NICU. If infants are in the M-MILK group, M-MILK will begin on day 3 of life after every hands-on care and during the beginning of a full gavage feeding. We will measure outcomes using validated methodologies at baseline (enrollment), 34 weeks PMA, discharge, and 2 months CA.

b. Setting

The M-MILK pilot study will be conducted in a level III NICU at LUMC (Maywood, IL). The hospital provides care to families with diverse racial, ethnic, and socioeconomic backgrounds. The nursing staff are predominantly registered nurses and advanced nurse practitioners, and the physicians are board certified

neonatologists. Infants are fed using mother's own milk, donor milk, and/or formula. However, we will only include infants who receive mother's own milk or donor's milk.

c. Sample

We will enroll 12 preterm infants (6 per group). Anticipated a 40% attrition rate, we expect the final sample size to be 12 preterm infants. Estimates of average values and variability of continuous measures are acceptable at this sample size using the "rule of 12" as recommended.³¹

VII. Study Procedures

a. Subject Selection Procedures

i. Inclusion/Exclusion Criteria

Inclusion criteria

- Born between 22 to 33 weeks gestational age
- Mother is pumping and infant is receiving mother's own milk and/or donor's milk to be in the intervention group.

Exclusion criteria

- Congenital abnormalities in the digestive, e.g., clef lip and palate, omphalocele
- Necrotizing enterocolitis
- Congenital heart disease that requires surgery

ii. Screening procedures

After infants are admitted to the NICU, we will review their electronic medical records to screen for eligible infants according to the inclusion and exclusion criteria. Once an infant is enrolled into the study, the screening period continues until NICU discharge. The infant will be classified as screen failed and excluded if he/she develops any of the exclusion criteria.

iii. Recruitment Procedures

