Parents of eligible infants will be approached during their post-partum hospitalization or in the NICU at LUMC. A research team member will provide details regarding the study purpose, procedures, and answer questions. Parents will be provided with a study brochure. If parents request additional time to make their decision, we will request a phone number and ask permission to follow-up. If parents agree to have their infant participate, a written informed consent and authorization to use and disclose the PHI will be obtained. Parents will receive a copy of their signed informed consent and authorization to use and disclose the PHI. A copy of the informed consent form will be uploaded to the infant's electronic medical record. The original signed consent will be stored in a locked cabinet at LUC CTRE (Maywood, IL). Infant's participation in the study will end after the phone/Zoom interview at 2 months CA. We will provide a \$50 incentive e-gift card at NICU discharge and a \$50 incentive e-gift card at the completion of the post-discharge follow-up, a total of \$100 e-gift card. Premature infants, by virtue of their age, are unable to give consent or assent, and therefore, will not give assent or participate in the informed consent process.

iv. Randomization Procedures

Randomization is controlled by using two computer-generated lists of random numbers that are corresponded to each group: Group 1 (M-MILK) and Group 2 (attention control), balanced so that 1/2 of the infants are in each group. The lists are retained. The random numbers will be printed in order on small cards stated as Group 1 or Group 2. The cards will be placed in envelopes and placed in order in a box. Prior to approaching parents for recruitment, we will open the first envelope in the box to obtain the group assignment. We will request parents to not disclose their group assignment with other parents in the NICU. The research team

members, staff nurses, and parents cannot be blinded to the treatment condition. The research team members need to know which intervention to provide. Staff nurses provide direct care to infants. The two groups are described in the consent form as required by LUC Institutional Review Board.

v. Study Intervention

1. MMILK Intervention

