
	continuous measure based on total percent of methylation for each NR3C1 and HSD11B2 promoter region as well as for each individual CpG site.	
Gut Microbiome	
Infant fecal samples will be collected by a bedside nurse in the NICU at baseline, 34 weeks PMA, NICU discharge. For the 2 months CA sample, parents will receive a fecal collection kit with written instructions to collect and send samples to our lab via USPS postal services.
 
Fecal samples from each infant will be collected using sterile, disposable spatulas during diaper changes and then placed into a sterile specimen container with microbial DNA stabilizer solution for 60 days at room temperature. The samples collected will be transported to a laboratory at the Loyola University Chicago Center for Translational Research and Education (Maywood, IL). All samples will be stored at room temperature. Monthly, the buccal swab samples will be securely transported in a biospecimen transfer container (Saf T Pak, Austell, GA) via car to Rush University Medical Center Genomics and Microbiome Core Facility (Chicago, IL) for processing and analyses. Genomic DNA will be extracted from fecal material using a Maxwell RSC48 autM-MILKted extraction device (Promega) and employing a Maxwell RSC Fecal Microbiome DNA kit, as described previously.⁶⁴ Samples will be subject to physical shearing (i.e., bead-beating) using a TissueLyser II device (Qiagen) prior to extraction. Genomic DNA will be prepared for sequencing using a two-stage amplicon sequencing workflow⁶⁵ and employing primers 515F-modified and 806r-modified.⁶⁶ Sequencing will be performed a MiniSeq sequencer (Illumina)⁶⁴ with paired-end 2x154 base sequencing. Basic processing of sequence data, including merging of forward and reverse reads, quality and primer trimming, chimera removal, and selection and annotation of amplicon sequence variants (ASVs) will be performed.⁶⁴ Alpha diversity indices (e.g., Shannon index) will be calculated on rarefied datasets⁶⁷ in R using the vegan library package.⁶⁸ Pairwise comparisons of alpha diversity indices will be performed using the non-parametric Mann–Whitney test. Beta diversity analyses will be performed on pairwise Bray–Curtis indices calculated in R using the metaMDSdist function in the vegan library v2.5-6. The dissimilarity indices will be modelled and tested for significance with the sample covariates using PERMANOVA.⁶⁹ Differential abundance analyses of individual taxa between groups will be performed using the software package DESeq2, generating an FDR q-value.⁷⁰ DESeq2 has been shown to be appropriate for differential abundance comparisons in studies with small sample size groups (< 20) or unbalanced design.⁷¹ To identify taxa that most strongly explain between-group differences, a Linear discriminant analysis Effect Size (LEfSe) analysis will performed.⁷¹
	T0, T1, T3, T4 Fecal samples

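### If 12 infants are enrolled and 40–50% are lost by 2 months corrected age, an exact two-sided Mann–Whitney test of T4 alpha diversity cannot reach 0.05; the enrolled and final N need reconciling first.

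*Combined protocol and SAP*

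**What the plan says.** **Test.** Table 1 (Section VII.a.vi.1, Gut Microbiome row): "Pairwise comparisons of alpha diversity indices will be performed using the non-parametric" Mann–Whitney test. The row lists fecal samples at T0, T1, T3 and T4; parents collect the T4 sample and post it. It does not say which groups or time points are paired, and gives no alpha, sidedness or choice between exact and approximate p-values. It also plans PERMANOVA, DESeq2 and LEfSe.

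**Sample size.** Sections III, VI.a and VI.c give 12 infants, 6 per arm. Section VI.c continues: "Anticipated a 40% attrition rate, we expect the final sample size to be 12 preterm infants". The abstract differs: "We propose the M-MILK pilot study (N = 20): a 2-group, 10 per group, parallel design". Section VII.a.iv describes allocation as "balanced so that 1/2 of the infants are in each group".

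**Follow-up.** Section IV counts retention after discharge as feasible if "at least 50% of infants completed post-discharge follow-ups".

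**Purpose.** Section IV names feasibility, acceptability, variability data for sizing the later trial, and costs. Section IX plans descriptive statistics for all variables of interest.

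**The concern.** A rank test has a smallest attainable p-value, fixed by the two group sizes. If that value exceeds the significance level, the test cannot reject even when every infant in one arm ranks above every infant in the other. With 12 enrolled and the anticipated loss, the T4 comparison may fall in that range.

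A non-significant T4 result would then reflect the number of infants and not M-MILK, and the plan does not say how such a result should be read. The pilot needs the spread of the T4 values and a rough arm difference, and a test that cannot reject gives neither.

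**Working it through.** **1. The plan's own figure.** Expected final n = enrolled × (1 − attrition).

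- 12 × (1 − 0.40) = 7.2, not the stated 12.
- 20 × (1 − 0.40) = 12.0, and 12 / (1 − 0.40) = 20.

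The stated final 12 reproduces only from the abstract's 20.

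**2. Infants with T4 data if 12 are enrolled.** At 40% loss, about 7. At the 50% feasibility floor, 12 × 0.50 = 6. Usable samples could be fewer than completed interviews, since the kit must be posted back.

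**3. Smallest attainable p.** Without ties, the most extreme result is complete separation, so the two-sided exact minimum is 2 / C(n1 + n2, n1). Alpha is taken as 0.05 (assumption).

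| With T4 data | Split | Smallest two-sided exact p |
|---|---|---|
| 6 | 3 v 3 | 2/20 = 0.100 |
| 6 | 4 v 2 | 2/15 = 0.133 |
| 6 | 5 v 1 | 2/6 = 0.333 |
| 7 | 4 v 3 | 2/35 = 0.057 |
| 7 | 5 v 2 | 2/21 = 0.095 |
| 7 | 6 v 1 | 2/7 = 0.286 |
| 8 | 4 v 4 | 2/70 = 0.029 |
| 8 | 5 v 3 | 2/56 = 0.036 |
| 8 | 6 v 2 | 2/28 = 0.071 |
| 12 | 6 v 6 | 2/924 = 0.002 |

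Every split of 6 or 7 exceeds 0.05; 4 v 4 and 5 v 3 do not. At those two splits only complete separation is enough: one overlapping pair doubles p to 4/70 = 0.057 or 4/56 = 0.071.

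**4. Other p-value methods**

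| Method | 4 v 3 | 3 v 3 |
|---|---|---|
| Normal approximation with continuity correction, no ties | 0.052 | 0.081 |
| Normal approximation without correction | 0.034 | 0.0495 |
| One-sided exact | 0.029 | 0.050 |

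Ties can also move the corrected approximation: one tied pair in the group of 4 brings 4 v 3 to 0.0497.

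**5. How often 0.05 is attainable.** Assume that each infant is retained independently with probability r, and sum the two binomial distributions over all splits with 2 / C(n1 + n2, n1) ≤ 0.05.

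- 12 enrolled: about 43% at r = 0.6 and 19% at r = 0.5.
- 20 enrolled: about 97% at r = 0.6.

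**6. PERMANOVA.** With unequal groups, only one labelling reproduces complete separation, so the permutation minimum is 1/35 = 0.029 at 4 v 3 and 1/21 = 0.048 at 5 v 2. With equal groups, swapping the labels gives the same statistic, so 3 v 3 has 2/20 = 0.10. The limit therefore bites at 3 v 3 but not at 4 v 3 or 5 v 2.

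**The case against.** A reader might infer that, on the protocol's own numbers, the T4 test can never be significant. The documents do not support that, for four reasons.

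- The Section VI.c sentence that gives 40% attrition also expects a final 12, and at 6 v 6 the minimum is 0.002. Section X adds a third figure: 2 infants a month for 9 months is 18, at which 0.05 is attainable in about 92% of trials at 60% retention. The count of 7 comes from taking one side of a contradiction.
- Forty percent is an expectation and 50% a floor, not fixed counts. One more infant than 7 reverses the result at 4 v 4 or 5 v 3.
- Alpha, sidedness and p-value method are not stated, and step 4 shows that some choices cross 0.05.
- A between-arm test at T4 is a reading of Table 1, which does not name what is paired.

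These points stand, and they make the finding conditional. They do not remove it: the final 12 cannot follow from 12 enrolled, and at 8 infants the test rejects only on complete separation. That the answer can turn on an unspecified p-value method is itself a reason to settle the text.

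A reader might also infer that every T4 microbiome test should go. PERMANOVA can reach 0.05 at 4 v 3 and 5 v 2, and nothing here counts against DESeq2 or LEfSe.

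Finally, no aim or feasibility criterion depends on a microbiome p-value, Section IX already plans descriptive statistics, and nothing in the plan proposes reading non-significance as no effect. This limits the consequence.

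**Conclusion.** The point holds conditionally. The firm part is that 12 enrolled, 40% attrition and a final 12 are incompatible: 12 enrolled leaves about 7, and a final 12 needs 20.

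The conditional part is that, with 12 enrolled and 40–50% lost by T4, a between-arm two-sided exact Mann–Whitney test of alpha diversity cannot fall below 0.057 with 7 infants or 0.100 with 6. It rests on an assumed alpha of 0.05, an exact two-sided p-value, and a between-arm comparison at T4. Under independent retention, the test has some chance of reaching 0.05 in about 43% or 19% of trials (60% or 50% retention), so failure is likely but not certain. With 20 enrolled at 60% retention the problem largely disappears (about 97%).

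The effect on the pilot's stated aims is modest. The change is worth making because it costs little and gives the variability information that the pilot is meant to supply.

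**What to change.** 1. Reconcile the enrolled and final N across the abstract and Sections III, VI.a and VI.c, check them against the accrual rate in Section X, and restate the expected number with T4 data (about 7 if 12 are enrolled).
2. In the Gut Microbiome row, say which arms and time points are compared, and give the alpha, sidedness and p-value method.
3. For T4 alpha diversity, report individual values, group median and SD, and the Hodges–Lehmann arm difference with the exact interval level that the retained n allows: 1 − 2/20 = 90% at 3 v 3, and 1 − 2/35, about 94%, at 4 v 3. Use this in place of a Mann–Whitney p-value whenever the smallest attainable p exceeds 0.05.
4. Apply the same rule to PERMANOVA only where its permutation minimum exceeds 0.05, for example 3 v 3. Keep the other T4 microbiome analyses and label them exploratory.
5. State in Section IX that non-significance at T4 is not evidence of no effect.

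The cost is wording in Table 1, Section IX and the sample-size statements, with no added samples; adding infants is not required. The downside is that no T4 alpha-diversity p-value is reported when retention is that low.
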